- cc Hidradenitis Suppurativa Clinical Parameters will be performed at each designated study visit and must address all relevant anatomical regions in each participant; the number, location, longest distance between relevant lesions, and whether the lesions are separated by normal-appearing skin will be measured in each anatomical area; Hurley Stage is included as an assessment performed during the HS clinical parameters; Hidradenitis Suppurativa Physician's Global Assessment is included as an assessment performed during the HS clinical parameters. The site is responsible for counting lesions that received intervention as permanently present in the lesion counts from the date of the intervention. The data collected from the HS clinical parameters will be used for the derivation of the HiSCR50, HiSCR75, HiSCR90, IHS4, AN count, Hidradenitis Suppurativa Physician's Global Assessment, raw counts, and disease flares. For each participant it is recommended that the HS Clinical Parameters is assessed by the same Investigator during the entire study if possible.
- dd [REDACTED]
- ee The participant should complete the questionnaire before site personnel perform any clinic assessments and before any interaction with the site personnel has occurred to avoid biasing the participant's response.
- ff Number of samples (tubes) and quantity of biological samples needed for each assessment can be found in the laboratory manual.
- gg Up to 4 hours prior to IMP administration.
- hh PD biomarkers will include serum TNF and serum OX40L.
- ii Optional assessment with skin biopsies at Baseline (Visit 2) and Week 16 (Visit 10) will be performed. Participants without history of hypertrophic or keloid scarring as assessed by the Investigator through participant interview and review of medical history can choose whether they would like to participate in optional assessment. If they consent to participate, the participants will have one lesional biopsy of an inflammatory nodule and one non-lesional biopsy at Baseline (Visit 2) and Week 16 (Visit 10) (for a total of 4 biopsies). Biopsy is to be performed after HS clinical parameters, but before IMP administration at study visit. Sutures may be placed per the discretion of the Investigator. Participants will be scheduled for an additional visit 1 week after skin biopsy for suture removal if sutures are placed per the discretion of the Investigator. Sample will be processed per instructions in the laboratory manual.
- jj Biomarker panel will include, but is not limited to, CRP, hs-CRP, [REDACTED], SAA, and ANC. Hematology sample will be drawn for neutrophils (with other values reported per laboratory manual).
- kk Optional sample collected for potential retrospective safety follow-up and/or additional exploratory analysis.

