### Overall design synopsis:

This is a multinational, multi-center, randomized, double-blind, placebo-controlled, Phase 2a proof of concept study to evaluate the efficacy and safety of SAR442970 in adult participants with moderate to severe HS.

The intervention in the study includes investigational medicinal product (IMP) administration every 2 weeks (Q2W) to complete 28 weeks of treatment with SAR442970. The study is

composed of 3 parts: a double-blind, placebo-controlled period (Period A), followed by an open-label period (Period B), and then followed by a safety Follow-up Period (Period C).

Participants will receive SAR442970 150 milligrams (mg) or matching placebo Q2W at the Week 0 visit up to the Week 14 visit as part of Period A, the double-blind, placebo-controlled period. Beginning at the Week 16 visit, all participants will receive SAR442970 150 mg Q2W up to the visit prior to the individual participant's end of treatment (EOT) visit as part of Period B, the open-label period. Period C will be an 8-week safety Follow-up Period commencing with the End of Treatment (EOT) visit and concluding with the End of Study (EOS) visit. Participants will not be expected to receive more than 14 doses of SAR442970. [For participants in the US, response will be assessed at the Week 20 visit (see definition of response in [Section 4.1](#)). Responders at Week 20 will continue in Period B to complete the 12-week open-label period. Non-responders at Week 20 will move directly to the safety follow-up period (Period C) with the Week 20 visit serving as their EOT visit. No IMP will be administered to non-responders at their EOT visit at Week 20].

The target population of the study is participants with HS based on a history of signs and symptoms consistent with HS for at least 1 year prior to Baseline and demonstrating moderate to severe disease at Baseline as defined by HS lesions present in at least 2 distinct anatomic areas (eg, left and right axilla; or left axilla and left inguino-crural fold), one of which must be Hurley Stage II or Hurley Stage III, an abscess and inflammatory nodule (AN) count of  $\geq 3$ , a draining tunnel count  $\leq 20$ , and C-reactive protein (CRP) level of  $> 3$  mg/L.

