| Prior and Concomitant Medications                               | X   | X h, i   | X         | X         | X         | X         | X         | X         | X         | X          | X                | X  | X  | X          | X                | X                | X                |  |   |
| Resume HS Medication if Needed w                     |   |   |           |           |           |           |           |           |           |            |                  |  |  |            |                  | X                |                  |  |   |
| Safety   |   |   |           |           |           |           |           |           |           |            |                  |  |  |            |                  |                  |                  |  |   |
| AE Reporting, Including SAEs                                    | X   | X   | X         | X         | X         | X         | X         | X         | X         | X          | X                | X  | X  | X          | X                | X                | X                |  |   |
| 12-Lead ECG   | X   |   |           |           |           |           |           |           |           |            | X                |  |  |            |                  | X                | X                |  |   |
| Vital Signs x  | X   | X   | X         | X         | X         | X         | X         | X         | X         | X          | X                | X  | X  | X          | X                | X                | X                |  |   |
| Physical Examination (including height and weight) y | X   | X   |           | X         |           | X         |           | X         |           | X          |                  | X  |  | X          |                  | X                | X                |  |   |
| Fasting Lipid Panel z                                | X   | X   |           | X         |           | X         |           |           |           | X          |                  | X  |  |            | X                |                  | X                |  |   |

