| Visit Days  | D-28 to D-1                                     | D1  | D15 (±3d) | D29 (±3d) | D43 (±3d) | D57 (±3d) | D71 (±3d) | D85 (±3d) | D99 (±3d) | D113 (±3d) | D127 (±3d)       |   | D141 (±3d)                                       | D155 (±3d)                                | D169 (±3d)  | D183 (±3d)       | (±3d)  | (±5d)   |  |
| Daily Analgesic Usage Diary t                        | ←-----→   |   |           |           |           |           |           |           |           |            |                  |   |  | ←-----→                                   |   |                  |  |   |  |
| Prior and Concomitant Medications                               | X   | X i,j  | X         | X         | X         | X         | X         | X         | X         | X          | X                |   | X  | X   | X   | X                | X  | X   |  |
| Resume HS Medication if Needed x                     |   |   |           |           |           |           |           |           |           |            |                  |   |  |   |   |                  | X  |   |  |
| Safety   |   |   |           |           |           |           |           |           |           |            |                  |   |  |   |   |                  |  |   |  |
| AE Reporting, Including SAEs                                    | X   | X   | X         | X         | X         | X         | X         | X         | X         | X          | X                |   | X  | X   | X   | X                | X  | X   |  |
| 12-Lead ECG   | X   |   |           |           |           |           |           |           |           |            | X                |   |  |   |   |                  | X  | X   |  |
| Vital Signs y  | X   | X   | X         | X         | X         | X         | X         | X         | X         | X          | X                |   | X  | X   | X   | X                | X  | X   |  |
| Physical Examination (including height and weight) z | X   | X   |           | X         |           | X         |           | X         |           | X          |                  |   |  | X   |   | X                | X  | X   |  |

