- e* Participants who discontinue IMP treatment prior to completing the treatment period and 8-week Follow-up Period will be evaluated as soon as possible at the individual participant's EOT Visit, using procedures as planned for the EOT Visit. At their EOT Visit, participants will resume their HS medications or other appropriate therapy as needed per Investigator discretion after the EOT study assessments have been performed and will enter the 8-week safety Follow-up Period, concluding with EOS Visit.
- f* The study visits occur on the planned dates (relative to the first IMP), as scheduled.
- g* Visits at Week 18, 22, and 26 may be performed with a home nursing service.
- h* To qualify for randomization all inclusion criteria and none of the exclusion criteria are met by the participant.
- i* Update inclusion/exclusion criteria, medical and surgical history, and prior and concomitant medications information to assure participant eligibility.
- j* Prior to randomization.
- k* Investigators must obtain a history of prior therapies used to treat HS, including antibiotics. The prior doses and reasons for discontinuation of antibiotic therapy will need to be recorded in the eCRF to verify eligibility. In the TNF-experienced population, Investigators will be asked to complete a questionnaire on the duration of anti-TNF therapy use as well as providing a description of the treatment response to anti-TNF therapy.
- l* Investigators will be asked to complete a questionnaire on participant's family history of HS in first-degree relatives (parents, siblings, and children) to be recorded in the eCRF.

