| Secondary 

• To evaluate the efficacy and safety of SAR442970 in the biologic and small molecule immunosuppressive-naïve subgroup of participants with HS

• To evaluate the effect of SAR442970 on pain in the biologic and small molecule immunosuppressive-naïve subgroup of participants with HS

• To evaluate the pharmacokinetics (PK) of SAR442970 and anti-drug antibodies to SAR442970 in the biologic and small molecule immunosuppressive-naïve subgroup of participants with HS

 | 

• Time to onset of achieving HiSCR50

• Percentage of participants achieving HiSCR75 (defined as ≥75% reduction from Baseline in the total AN count, with no increase from Baseline in abscess or draining tunnel count) at Week 16

• Percentage of participants achieving HiSCR90 (defined as ≥90% reduction from Baseline in the total AN count, with no increase from Baseline in abscess or draining tunnel count) at Week 16

• Percentage of participants who experience improvement by at least one International Hidradenitis Suppurativa Severity Score System (IHS4) stage at Week 16 (See also Section 8.2.1.3 for definition of IHS4)

• Change in absolute score from Baseline in IHS4 at Week 16

• Percentage of participants who experience a flare, defined as at least a 25% increase in AN count (with a minimum increase of 2) relative to Baseline at Week 16 (See also Section 8.2.1.4 for definition of flare)

• Percentage of participants achieving IHS4-55 at Week 16 (defined as achievement of a 55% reduction in IHS4 score from Baseline)

• Incidence of treatment-emergent adverse events (TEAEs), adverse events of special interest (AESIs), and serious adverse events (SAEs) including local reactions

• Incidence of potentially clinically significant abnormalities in laboratory tests, vital signs, and electrocardiograms

• Percentage of participants achieving at least 30% reduction and at least 1 unit reduction from Baseline in weekly average of daily [REDACTED]
[REDACTED]
[REDACTED]
[REDACTED]
[REDACTED]

• Serum SAR442970 concentrations throughout the study

• Incidence of anti-SAR442970 antibody positive response throughout the study

 |

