### 7.1.3 QTc stopping criteria

Administration of study drug should be interrupted if a participant meets either bulleted criterion:

- QTc >500 msec confirmed by repeat measurement or manual over-read.
- QTc increase from Baseline >60 msec.

If a clinically significant finding is identified (including, but not limited to changes from Baseline in QT interval corrected using formula (QTcF) after enrollment, the Investigator or qualified designee will determine if the participant can continue on the study intervention and if any change in participant management is needed). This review of the ECG printed at the time of collection must be documented. Any new clinically relevant finding should be reported as an AE.

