2 STATISTICAL ANALYSES

2.1 GENERAL CONSIDERATIONS

In general, continuous data will be summarized using the number of observations available, mean, standard deviation (SD), median, Q1, Q3, minimum, and maximum. Categorical and ordinal data will be summarized using the count and percentage of participants.

The baseline value is defined as the last available value before the first dose of double-blind IMP. For participants randomized but not treated, the baseline value is defined as the last available value before randomization.

Unless otherwise specified, analyses will be performed by intervention group and overall, for baseline and demographics characteristics.

The intervention groups will be presented as follows:

- Period A: SAR442970 150mg q2w and Placebo.
- Period B and Period C: SAR442970 150 mg q2w/SAR442970 150 mg q2w, Placebo/SAR442970 150 mg q2w and overall unless otherwise specified.

Observation period

The observation period will be divided into the following segments:

The pre-treatment period is defined as the period up to first blinded IMP administration.

Period A:

- The **treatment-emergent (TE) period of Period A** is defined as the period from the first blinded IMP administration to the last blinded IMP administration + 75 days or the first open-label IMP administration, whichever occurs earlier. The TE period of Period A includes the following 2 sub-periods:
 - The **on-treatment period of Period A** is defined as the period from the first blinded IMP administration to the last blinded administration of the IMP + 14 days, or the first open-label IMP administration, whichever occurs earlier.
 - The **residual treatment period of Period A** is defined as the period after the end of the on-treatment period of Period A to the end of the TE period of Period A.

Period B:

- The **treatment-emergent (TE) period of Period B** is defined as the period from the first open-label IMP administration to the last open-label IMP administration + 75 days. The TE period of Period B includes the following 2 sub-periods:
 - The **on-treatment period of Period B** is defined as the period from the first open-label IMP administration to the last open-label administration of the IMP + 14 days.

- The **residual treatment period of Period B** is defined as the period after the end of the on-treatment period of Period B to the end of the TE period of Period B.

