2.7 SAFETY ANALYSES

All safety analyses will be performed for Period A and Period B separately, on the safety populations as defined in [Section 1.3](#), unless otherwise specified, using the following common rules:

- The analysis of the safety variables will be essentially descriptive, and no statistical testing is planned.
- Safety data in participants who do not belong to the safety population (e.g., exposed but not randomized) will be provided separately.

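### As printed, both flowcharts put the only mid-study ECG at Week 18, after open-label dosing starts, so participants who complete Period A would have no scheduled post-baseline ECG in the randomised phase

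*Protocol*

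**What the plan says.** The ECG row in Protocol 1.3.2 (United States) reads "12-Lead ECG | X | | | | | | | | | | X | | | | | | X | X". The row in 1.3.1 (all other countries) reads "12-Lead ECG | X | | | | | | | | | | X | | | | | X | X". Protocol 8.3.3 gives no weeks and refers to the schedule of activities.

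On treatment, the synopsis says: "Beginning at the Week 16 visit, all participants will receive SAR442970 150 mg Q2W". Week 18 is one of three visits that need not be on site: "Visits at Week 18, 22, and 26 may be performed with a home nursing service".

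On the endpoint, Protocol Table 2 lists as secondary: "Incidence of potentially clinically significant abnormalities in laboratory tests, vital signs, and electrocardiograms". SAP 2.7 adds: "All safety analyses will be performed for Period A and Period B separately". SAP 2.1 ends the Period A treatment-emergent period at "last blinded IMP administration + 75 days or the first open-label IMP administration, whichever occurs earlier". SAP 2.7.3.1 plans two ECG outputs: change from baseline by analysis window in the on-treatment period, and incidence of potentially clinically significant abnormalities (PCSAs) in the treatment-emergent period. SAP Table 12 has a Week 16 ECG window running from day 106 to the first open-label dose.

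**The concern.** The only randomised contrast between SAR442970 and placebo is in Period A. From Week 16, those who continue all receive active drug. An ECG first taken at Week 18 compares people on continued SAR442970 with people who have just switched to it. It cannot say how often ECG abnormalities arise on drug relative to placebo.

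The SAP nevertheless plans Period A ECG tables. On this schedule they would be nearly empty for participants who complete the period, and would be filled by those who stopped early or had an ECG for some clinical reason. The QTc criteria in Protocol 7.1.3, one of which is "QTc increase from Baseline >60 msec", would likewise have no scheduled ECG to act on in Period A for those participants.

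**Working it through.** The plan states no figure to reproduce. The check is a column count, a test of how far the columns can be trusted, and day arithmetic.

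**1. Column count.** In the visit-week header of both flowcharts, Screening is column 1, Week 0 is column 2, Week 16 is column 10 and Week 18 is column 11. EOT and EOS are columns 16 and 17 in 1.3.1. They are columns 17 and 18 in 1.3.2, which has an extra Week 20 response column.
- Non-US ECG crosses: columns 1, 11, 16, 17, which are Screening, Week 18, EOT and EOS.
- US ECG crosses: columns 1, 11, 17, 18, which are the same four visits.

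Neither table shows an ECG from Week 0 to Week 16. The Screening ECG therefore serves as baseline.

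**2. Can the column position be trusted?** Several rows are displaced in the text version of these tables:
- US anti-drug antibodies read Week 18, Week 26 and EOT. SAP 2.8.2 and the non-US row give Week 16, Week 28/EOT and EOS.
- US physical examination reads Weeks 22 and 26. Protocol 10.8.2 says Weeks 20 and 24.
- Non-US fasting lipids read Week 26 and are blank at Week 28. The US row has EOT.
- Urinalysis reads Week 6 in the non-US table and Week 8 in the US table.
- PK reads Week 10 in the non-US table and Week 14 in the US table. SAP Table 15 has a Week 10 PK window.
- The non-US pregnancy test is blank at Week 28, although its footnote requires a test at every visit. The US row has EOT.
- In the non-US table, the heading for the end of double-blind treatment sits over Week 20.

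Other rows can be verified and are correctly placed:
- The IMP diary row falls at Weeks 18, 22 and 26, the home-nursing weeks, in both tables. Its first cross is in the same column as the ECG cross.
- The row for resuming HS medication falls at EOT in both tables.
- Non-US physical examination falls at Weeks 4, 8, 12, 16, 20, 24, 28 and 36. The US row is right up to Week 16.

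The row slips listed above all appear as a disagreement between the two flowcharts. The ECG rows agree with each other, and their EOT and EOS crosses are in the right place. The US antibody row, which does turn Week 16 into Week 18, also misplaces its later crosses. Week 18 is therefore the better reading, but it is not proved.

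**3. Which period does a Week 18 ECG fall in?** Week 16 is day 113 ± 3 (110 to 116). Week 18 is day 127 ± 3 (124 to 130). If open-label dosing starts at the Week 16 visit, the Week 18 ECG falls on these Period B days:
- earliest: 124 − 116 + 1 = 9
- latest: 130 − 110 + 1 = 21

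The Period B Week 18 window in SAP Table 12 is days 2 to 21, so this ECG cannot count in Period A.

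**4. Size.** Planned arms are 84 × 2/3 = 56 on SAR442970 and 84 × 1/3 = 28 on placebo. Those who complete Period A have 0 scheduled post-baseline ECGs in it. A SAR442970 participant who misses no dose receives 9 (Weeks 0, 2, 4, 6, 8, 10, 12, 14, 16) before the first scheduled on-treatment ECG.

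**5. What would still populate Period A?** Participants who stop early have the EOT procedures, which include an ECG, and a further ECG at EOS. SAP 2.7.3.1 counts unscheduled and repeated measurements for PCSAs. For change from baseline, the on-treatment period ends 14 days after the last blinded dose, so an early EOT ECG counts only if taken by then.

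**The case against.** The strongest reply is that the point hangs on one column position in tables that are visibly displaced elsewhere, with no running text to confirm it. One US row does show a Week 16 cross landing in the Week 18 column. The laboratory tests, lipids, urinalysis, C-SSRS and physical examination are all at the on-site Week 16 visit, where an ECG would sit naturally, and Week 18 may be a home visit. This stands as a reason to check the source flowcharts first. It does not overturn Week 18 as the better reading, because the two ECG rows agree and show none of the other signs of slippage. The Week 16 ECG window in SAP Table 12 does not settle it either way, since that table gives every safety variable the same windows.

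A second reply is that Period A would not be empty and that the safety analysis is descriptive, with no testing planned. Both are true. A reader might infer that every placebo participant has switched before the ECG and that no placebo comparison of any kind exists. The documents do not support that. Placebo participants who stop in Period A never start open-label drug, and early-EOT and unscheduled ECGs enter the PCSA tables by arm. But those ECGs come from participants selected by stopping or by a clinical event, so they do not restore the randomised comparison that a scheduled visit would give.

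**Conclusion.** The point holds conditionally. As printed, the one scheduled ECG between Screening and EOT is at Week 18 in both flowcharts, after all who continue have started open-label SAR442970. If the source flowcharts confirm this, participants who complete Period A have no scheduled post-baseline ECG there in either arm. The Period A change-from-baseline and PCSA tables would then offer no scheduled randomised comparison for a stated secondary safety endpoint.

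This assumes that the ECG cross is read in the right column and that open-label dosing starts at the Week 16 visit. If the source shows Week 16, the point falls. It does not bear on the primary endpoint or the sample size. It is a cheap improvement to the safety data, with moderate confidence in the Week 18 reading.

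**What to change.** First, confirm the ECG visit in the source version of both flowcharts.

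If it is Week 18, move the mid-study 12-lead ECG in Protocol 1.3.1 and 1.3.2 to the on-site Week 16 visit, before the first open-label dose. It then falls in the existing Week 16 window of SAP Table 12, in Period A, and the SAP windows need no change.

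The cost is a protocol amendment moving one cross in two tables, with the number of ECGs unchanged. What is lost is the ECG two weeks after placebo participants switch to active drug. They still have ECGs at EOT and EOS. The first participant was randomised on 11-Jul-2023, so anyone already past Week 16 when the change takes effect stays on the old schedule, and the SAP should say how those participants are reported.

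If Week 18 is kept, add to SAP 2.7.3.1 that Period A contains no scheduled ECG, that its ECG tables come from early-EOT and unscheduled recordings, and that no placebo-controlled ECG conclusion will be drawn. That costs one or two sentences.
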